and data analysis and submit publications for peer review. These time estimations are plans that could be subject to change based on a number of external factors that may be out of our control. We plan to follow each subject clinically for a minimum of 24 months following implant, and to follow them for 12 more months for a minimum of 2 and a maximum of 4 research visits, and then clinically each year as long as they wish to remain implanted, and to assess needs for battery replacement. We plan to apply to CMS and Medicare for insurance coverage of the device implantation and battery replacement costs, and to apply to Medtronic for device donation (Medtronic has already reviewed this proposal in their scientific grants committee and approved donation of the devices and replacement devices).

6) Protocol: Methodology to be used - The study will be a prospective blinded design. Subjects will include ten individuals with medication refractory and severely disabling TS. We expect to consent and screen 50 individuals in order to enroll ten. A total of 6/10 subjects (60%) will need to be “responders” as a result of the intervention (YGTSS motor tic subscale reduction of $\geq 40\%$) for this study to reach effectiveness criteria.

Inclusion Criteria

- The diagnosis of TS must be made by both a fellowship-trained movement disorders neurologist and a psychiatrist and must meet Diagnostic and Statistical Manual of Mental Disorders (DSM-V) criteria for a diagnosis of TS.
- Yale Global Tic Severity Scale (YGTSS; 100) must be $\geq 35/50$ for at least 12 months and the motor tic subscore ≥ 15 . The TS must be causing incapacitation with severe distress, self-injurious behavior, and/or quality of life disruption.

OCD, Depression, and ADHD are not exclusionary[63-65] provided tics are the major difficulty requiring surgical intervention.

- There are no gender criteria for this study.

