Power Analysis: We will determine the effectiveness of DBS by comparing total tic score (YGTSS) at the six month time point to the pre-operative value for each subject. A 40% or greater reduction will be considered a successful response. The power to detect a statistical significance between a null proportion of 0.10 (this assumes that the true proportion of successful responders is 10%). The power analysis revealed that for an alternative proportion of .60 (i.e., 6 of 10 patients will show a

40% or greater reduction in motor tics at six months) there is a statistical power of 0.80 at an alpha level of .05. Therefore, we anticipate ten participants will be required for this study. The *power* procedure in Statistical Analysis Software (SAS), version 9.1 was used to conduct the power analysis. Data collected from this study will provide additional and currently unavailable data to inform power analysis of subsequent studies in Table 2 below.

Table 2. Power Analysis for Sample Size Effects

Table Power Analysis		Sample Size					
		8 patients		9 patients		10 patients	
Alternative proportion	Number of responders	Power	Number of responders	Power	Number of responders	Power	
.30	2	0.25	3	0.27	3	0.29	
.40	3	0.39	4	0.43	4	0.46	
.50	4	0.54	5	0.59	5	0.63	
.60	5	0.70	5	0.75	6	0.80	

General Analysis Approaches: The Wilcoxon signed rank test will be used to test for significant pre-post changes in numerical measures (e.g., YGTSS). Spearman correlations will be used to test relationships among numerical measures (e.g., neurocognitive measures, severity of tics and quality of life measures). Both the Wilcoxon signed rank and Spearman correlation tests are nonparametric procedures that are robust from data departures from normality and appropriate in the case of small sample sizes. All statistical tests will be two-sided and will be considered significant if p-values are less than 0.05. SAS software will be used to conduct all data analysis.

Specific Analysis Approach for Aim 1: We will determine the effectiveness of the “on condition” of DBS by comparing motor tic score (YGTSS) at the six month evaluation to the pre-operative value for each subject. A 40% or greater reduction will be considered a successful response. We will then test the hypothesis that the proportion of successful responders is greater or equal to (6/10) using the exact

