binomial test. We will compare the baseline motor YGTSS to the on DBS condition at six months (primary outcome). We will also perform comparisons of baseline to on/off/responsive conditions, and also comparisons of on/off conditions at six months as secondary analyses. To compare on versus off condition, we will form paired difference scores of YGTSS (YGTSS on minus YGTSS off) at six months and test for significance using the Wilcoxon signed rank test.

Specific Analysis Approach for Aim 2: We will first investigate rate and pattern changes in physiology and the possible correlation with clinical manifestation of motor tics by using exploratory data analysis techniques that will be graphical in nature. These exploratory techniques will include spectrograms and event related potentials. We will then conduct a preliminary time series analysis estimating fractal dimension, line length, and area-under-the-curve of the raw signal. The data obtained from these analyses will inform subsequent analysis and guide the development of statistical methods to analyze these types of data streams. Subsequent analysis will be more comprehensive, and will include time-frequency analysis of specific frequency bands, measures of coherence between channels containing movement related activity, and quantification of phase-amplitude coupling between frequency bands of interest. Any of these techniques has the potential to identify candidate predictors of tic onset.

Specific Analysis Approach for Aim 3: This protocol calls for testing an acute responsive DBS condition in subjects who reveal physiological predictors that can be set to sense tic by ECOG, and to respond to tic on the CM implanted device. It may also be possible to both sense and deliver stimulation from the CM DBS lead. Data will be analyzed using the Wilcoxon signed rank test. **We will collect physiology**

data and analyze the data, and test chronic responsive stimulation settings one month at a time for those subjects that respond well to the acute testion after Month 3.

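### The primary responder endpoint is defined on the YGTSS total tic score in some sections and on the motor score in others, so the 6/10 criterion can be met on one and missed on the other

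*Combined protocol and SAP*

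**What the plan says.** The response threshold is a 40% reduction at six months on DBS against the pre-operative baseline. The score it applies to changes between sections.

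**Total score (motor plus phonic)**
- Section 5, aim (1): the hypothesis is stated on motor and phonic tics together, with 6/10 as the target count.
- Section 7: the primary effectiveness variable is the total tic subscale.
- Section 12: the primary effectiveness outcome is the blinded rating of the combined score.
- Section 13, Power Analysis, first sentence: effectiveness is judged "by comparing total tic score (YGTSS) at the six month time point to the pre-operative value for each subject".

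**Motor score**
- Section 6: six of ten patients must respond "as a result of the intervention (YGTSS motor tic subscale reduction of" at least 40%), and this count is required "for this study to reach effectiveness criteria".
- Section 13, Power Analysis: the 0.60 alternative is explained as six of ten patients with a "40% or greater reduction in motor tics at six months".
- Section 13, Aim 1: effectiveness is judged "by comparing motor tic score (YGTSS) at the six month evaluation to the pre-operative value for each subject", followed by "We will then test the hypothesis that the proportion of successful responders is greater or equal to (6/10) using the exact" binomial test.
- Section 13, Aim 1, on the primary outcome: "We will compare the baseline motor YGTSS to the on DBS condition at six months (primary outcome").

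Within section 13 the sentence "A 40% or greater reduction will be considered a successful response" appears twice, once after the total score and once after the motor score.

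**The concern.** This is not loose wording for a single quantity. The YGTSS description in section 7 has motor and phonic tics rated separately, and the inclusion criteria set separate thresholds for the two (at least 35 of 50 overall, at least 15 for motor). The sections that define the primary outcome and the section that analyses it therefore name different variables. An analyst who follows Aim 1 would not analyse the outcome defined in sections 7 and 12.

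Both scores come from the same interview, so both responder counts will exist at month 6. If they fall on opposite sides of 6/10, the plan supports two primary results and does not say which counts. The choice could then be made after seeing both.

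**Working it through.** **1. The plan's own figure.** Section 13 gives power 0.80 for n = 10, null 0.10, alternative 0.60, alpha 0.05. A one-sided formula for two independent groups of 10 reproduces it:

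- pooled proportion (0.10 + 0.60)/2 = 0.35
- [0.50 × √10 − 1.645 × √(2 × 0.35 × 0.65)] / √(0.09 + 0.24) = (1.581 − 1.110)/0.574 = 0.82
- Φ(0.82) = 0.794

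The one-group exact test would give 0.945, rejecting at 4 or more responders; that mismatch is a separate matter. Here the inputs are proportions, so choosing one score changes neither the power nor the sample size. It changes who counts as a responder.

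**2. Single patients.** Section 7 gives five items per domain on a 6-point scale. Taken as 0–5, that is 0–25 per domain, which fits the 50-point total in section 6.

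| Patient | Motor | Phonic | Motor reduction | Total reduction |
|---|---|---|---|---|
| A | 20 → 12 | 20 → 20 | 8/20 = 40% (responder) | 8/40 = 20% (non-responder) |
| B | 20 → 14 | 20 → 8 | 6/20 = 30% (non-responder) | 18/40 = 45% (responder) |
| C | 20 → 12 | 15 → 12 | 8/20 = 40% (responder) | 11/35 = 31.4% (non-responder) |
| D | 20 → 13 | 15 → 6 | 7/20 = 35% (non-responder) | 16/35 = 45.7% (responder) |

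**3. Is this confined to unusual baselines?** No. Eligible integer baselines have motor 15–25, phonic 0–25 and total at least 35. Motor 15 allows 6 phonic values, motor 16 allows 7, and so on to 16 at motor 25, giving 6 + 7 + … + 16 = 121. Eligibility forces phonic to be at least 35 − 25 = 10.

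- Motor-only response: the smallest motor fall that reaches 40% is at most 10 points. With phonic unchanged, the total falls by at most 10/35 = 28.6%.
- Total-only response: let motor fall one point less than needed, and phonic fall to 0. The motor shortfall against 40% is at most 1 point, while phonic contributes a surplus of 0.6 × phonic, at least 6 points.

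Both directions are therefore reachable at all 121 baselines without either score worsening. This shows possibility, not frequency.

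**4. The trial verdict.** Take five patients who respond on both scores and four who respond on neither. If the tenth is like A or C, motor is 6/10 (met) and total 5/10 (missed). If the tenth is like B or D, motor is 5/10 (missed) and total 6/10 (met).

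**5. Significance.** Exact upper tail P(X ≥ r), n = 10, null 0.10:

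| Responders | One-sided p |
|---|---|
| 3 | 0.070 |
| 4 | 0.013 |
| 5 | 0.0016 |
| 6 | 0.00015 |

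The switch is between 3 and 4. Doubling the tail for the two-sided rule gives 0.140 and 0.026, the same switch.

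**6. Frequency, by assumption only.** The documents give no SD and no motor–phonic correlation. The simulation drew baselines uniformly from the 121, used bivariate normal percentage reductions, and rounded scores and kept them within 0–25. SD ran from 15 to 35 points and correlation from 0.3 to 0.9. Share of trials in which the 6/10 verdict differs:

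| Assumed mean reductions | Share |
|---|---|
| Equal, 40% or 45% | 12–28% |
| Motor 40–45%, phonic 30–45% | 12–53% |
| Motor 30–40%, phonic 40–45% | 8–31% |
| Equal, 20% | 0–4% |
| Equal, 60% | 0–11% |
| Equal, 70% | 0–3% |

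The 53% needs motor 45%, phonic 30%, SD 15 and correlation 0.3.

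**7. Effect of leaving the choice open.** A separate simulation used mean 46%, SD 25, baselines motor 20 and phonic 18, and correlations 0.3 to 0.9. Motor alone meets 6/10 in about 62% of trials; at least one of the two scores does in about 77% falling to 69%.

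**The case against.** - **The two sides are not evenly balanced.** Only sections 7 and 12 formally define the primary effectiveness outcome, and both use the total score. Some of the motor wording may be shorthand: the abstract describes aim 1 in terms of motor tics, and the primary-outcome label in Aim 1 may mainly mark the on-DBS condition. This stands as a reason to prefer total as the default. It does not resolve the conflict, because the section 6 criterion and the Aim 1 test name the motor score too specifically to be shorthand.

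- **Significance does not turn on 5 versus 6 responders.** This stands. The 3-versus-4 switch also assumes the 0.10 null of the power analysis. If the Aim 1 wording is read as a null of 0.60, 6/10 gives one-sided p = 0.63 and 5/10 gives 0.83, and the first significant count is 9/10 (p = 0.046). On neither reading does 5 versus 6 change significance. What changes is the effectiveness criterion in section 6.

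- **The frequencies rest on assumptions and span 0% to 53%.** This also stands; they are illustrative. The contradiction and the one-patient example do not depend on them.

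- **Clean prespecification may no longer be fully available.** Section 19 mentions data already collected from 6 TS patients with the predecessor device. The documents do not say whether these patients count toward the ten or had reached month 6. This is a reason for disclosure, not for leaving the score open.

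**Conclusion.** The concern holds and must be fixed. The variable that decides the study's effectiveness criterion is defined in two incompatible ways in the current text, and nothing reconciles them. One patient in ten can reverse the 6/10 result in either direction; that follows by arithmetic from the plan's definitions and a 0–25 range per domain. The effect is on the criterion, not on power, nor on significance at the 5-versus-6 boundary. The chance of conflicting verdicts is unknown from the documents. It is material if mean reductions lie near 40% (about 12–28% with equal means of 40% or 45%, under the stated assumptions) and small if they lie far from it.

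**What to change.** Name one YGTSS score as the primary responder variable before any further outcome data are examined. Use it in sections 5, 6, 7, 12 and 13, including the power analysis and Aim 1. Use the at-least-40% threshold throughout; section 5 currently asks for more than 40%.

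The sponsor must choose. The total score, rated blind at six months, is a reasonable default because sections 7 and 12 formally define it as primary. Since section 6 and the Aim 1 test point to motor, a short rationale is needed either way.

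Make the other score a named secondary analysis and report the responder count on both. State whether any six-month YGTSS results were known when the score was fixed, and whether the 6 patients mentioned in section 19 are among the ten.

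The cost is a wording amendment and one extra tabulation of scores already collected, with no new visits or measurements.

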(1) Test the hypothesis that centromedian (CM) continuous brain stimulation will be an effective and safe method for the treatment of tics in medication refractory TS. There is now a growing body of evidence supporting the use of DBS for tic suppression. Implantable brain stimulators provide a reversible and programmable solution to neuromodulation which are safer (no tissue destruction) and potentially more effective than ablative techniques such as thalamotomy, capsulotomy, and cingulotomy, especially because they can be performed bilaterally[62]. There are however important issues that may limit standard DBS effectiveness in this population including specific problems unique to this group of patients including the paroxysmal nature of the disorder. It would be desirable to design a therapy such as the one proposed in this grant application to neuromodulate only when needed (closed loop or responsive therapy). We plan to implant CM

thalamus and cortical ECOG bilaterally in 10 medication refractory TS subjects. We will employ a prospective blinded staggered onset design. We hypothesize that by using a chronic (continuous) stimulation strategy we will be able to achieve a greater than 40% reduction (over 6 months) in total tics (motor and phonic on the YGTSS) in more than $\frac{1}{2}$ of our subjects (6/10). We will in this study assess safety and also employ stopping rules to ensure subject safety.

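### The Aim 1 exact binomial test is tied to 6/10, the design alternative and success target, instead of the 0.10 null used for sizing; run as written, 6 of 10 responders gives p = 1.00

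*Combined protocol and SAP*

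**What the plan says.** All references are to the combined protocol and SAP.

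- **Section 13, Specific Analysis Approach for Aim 1.** A subject with a reduction of 40% or more is a responder. The plan will then "test the hypothesis that the proportion of successful responders is greater or equal to (6/10) using the exact" binomial test. No other proportion appears in that paragraph.
- **Section 13, Power Analysis.** The calculation is introduced with "The power to detect a statistical significance between a null proportion of 0.10". It continues "for an alternative proportion of .60 (i.e., 6 of 10 patients will show a" 40% or greater reduction, and concludes that "there is a statistical power of 0.80 at an alpha level of .05", with ten subjects.
- **Section 13, General Analysis Approaches.** "All statistical tests will be two-sided and will be considered significant if p-values are less than 0.05".
- **Section 6, Protocol.** "A total of 6/10 subjects (60%) will need to be" responders "for this study to reach effectiveness criteria".
- **Section 5, Purpose, aim (1).** The research hypothesis is a reduction of more than 40% in more than half of the subjects, given as 6/10.

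The figure 6/10 thus serves as research hypothesis, success criterion, design alternative and the value attached to the test. The figure 0.10 appears as a null only in the power paragraph.

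**The concern.** A test of a proportion needs a reference value that the data may reject. The power paragraph supplies one, 0.10. The sentence that specifies the test gives a different number, the alternative. An analyst who programs that sentence would enter 0.60, and a trial that does exactly what it was designed to do would then produce no evidence at all against the tested value.

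This is the only test stated for the responder proportion, which sections 7 and 12 make the basis of primary effectiveness. In a ten-subject single-arm study, the null is what gives a responder count inferential meaning. If the reference value is settled only after the count is known, that choice alone moves the p-value for 6/10 from 1.00 to 0.00015.

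**Working it through.** **Inputs.** n = 10, null 0.10, alternative 0.60, alpha 0.05, stated power 0.80 (section 13, Power Analysis); two-sided testing (General Analysis Approaches); success criterion of at least 6 of 10 (section 6). Let X be the number of responders, X ~ Binomial(10, p).

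**1. The plan's own figure.** For the exact single-arm test against 0.10:
- P(X ≥ 3 | 0.10) = 0.0702
- P(X ≥ 4 | 0.10) = 0.0128

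The critical value is 4, whether alpha is 0.05 one-sided or 0.025 per tail. Power is P(X ≥ 4 | 0.60) = 0.945. The probability of meeting the 6/10 criterion is P(X ≥ 6 | 0.60) = 0.633. Neither is 0.80.

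The figure does come out of a one-sided formula for two independent groups of ten, with pooled proportion (0.10 + 0.60)/2 = 0.35:
- null SE = √(2 × 0.35 × 0.65/10) = 0.2133
- alternative SE = √((0.09 + 0.24)/10) = 0.1817
- power = Φ[(0.50 − 1.645 × 0.2133)/0.1817] = Φ(0.821) = 0.794

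That formula matches all 12 cells of Table 2 to within 0.01. It is not the planned test.

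**2. The Aim 1 sentence run with 0.60 as the tested value.** For 6/10:
- upper tail = 0.2508 + 0.2150 + 0.1209 + 0.0403 + 0.0060 = 0.6331
- lower tail P(X ≤ 6) = 0.6177
- two-sided p = 1.00: six is the most likely count, and doubling the smaller tail exceeds 1

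| Responders | Upper tail vs 0.60 | Two-sided vs 0.60 (minimum likelihood) | Two-sided (doubled tail) |
|---|---|---|---|
| 6 | 0.633 | 1.00 | 1.00 |
| 7 | 0.382 | 0.749 | 0.765 |
| 8 | 0.167 | 0.334 | 0.335 |
| 9 | 0.046 | 0.059 | 0.093 |
| 10 | 0.006 | 0.0077 | 0.012 |

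Only 10/10 is significantly above 0.60 two-sided.

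**3. The same result against 0.10.** P(X ≥ 6 | 0.10) = 0.00015 (0.0003 doubled). Four responders give 0.0128 (0.0256 doubled); three give 0.0702 (0.1404 doubled). The exact 95% interval for 6/10 is 0.262 to 0.878, which excludes 0.10 and contains 0.60.

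**4. How often criterion and test would disagree if 0.60 is used.** Two-sided, disagreement means 6 to 9 responders: P(X ≥ 6) − P(X = 10). One-sided at 0.05, it means 6 to 8.

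| True rate | P(X ≥ 6) | Criterion met, not significant, two-sided | Share of criterion-meeting trials | One-sided |
|---|---|---|---|---|
| 0.40 | 0.166 | 0.166 | 99.9% | 0.165 |
| 0.60 | 0.633 | 0.627 | 99.0% | 0.587 |
| 0.70 | 0.850 | 0.821 | 96.7% | 0.700 |
| 0.80 | 0.967 | 0.860 | 88.9% | 0.591 |

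Against 0.10 the disagreement is zero: every count of 6 or more is significant.

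**5. The reverse reading.** If the sentence means a null of at least 0.60 with a lower-tail test, 6/10 gives p = 0.618 and is not rejected. But 3/10 gives 0.055 and is not rejected either, so non-rejection would not show efficacy.

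**The case against.** The best defence is that the sentence never calls 0.60 a null. A hypothesis that the proportion is at least the target reads naturally as the research hypothesis, in line with section 5. The same section names one null, 0.10, and labels 0.60 the alternative. Read together, the intended test is against 0.10, and p = 1.00 arises only by treating the stated alternative as the null. Effectiveness is in any case decided by a count in section 6, and a count of 6 or more is always significant against 0.10. Near-universal non-significance is also unsurprising when the true rate equals the tested value.

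Much of this is right. The intent is probably 0.10, the count criterion does not change, and the disagreement rates apply only if 0.60 is used. At true rates of 70% and 80%, though, above the tested value, the two-sided disagreement probability is still 0.821 and 0.860. The defence also asks the analyst to replace the number in the test sentence with one from another paragraph. The remaining readings do not help: a bare count rule is not a binomial test, and the lower-tail reading cannot demonstrate efficacy.

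Two further points are fair. The plan also assigns a Wilcoxon signed rank test to pre-post changes in YGTSS, and the Aim 1 paragraph labels the baseline to on-DBS comparison as primary; that test concerns the score, not the responder proportion. And section 6 defines response on the motor tic subscale while sections 7 and 12 use the total tic score. That conflict is separate, and naming the null does not resolve it.

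**Conclusion.** The concern holds. The test sentence and the sizing paragraph of section 13 conflict, and the conflict decides the reported result: for 6/10 responders, two-sided p = 1.00 against 0.60 and 0.00015 against 0.10. Followed as written, the plan would yield a non-significant responder test in 99% of criterion-meeting trials at a true 60% rate (0.627 of 0.633), and in 89% at a true 80% rate.

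These figures assume ten evaluable subjects, independent responses, the plan's two-sided 0.05 rule, and 0.60 as the tested value. The null is not absent from the document; it is missing from, and contradicted by, the sentence that specifies the test. The separate finding that 0.80 is not the power of the planned exact test (0.945) does not affect this conclusion.

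**What to change.** Replace the test sentence in the Aim 1 paragraph with:

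*The responder proportion will be tested against a null of 0.10 by the exact binomial test at two-sided alpha 0.05 (n = 10: significant in favour of DBS at 4 or more responders, upper-tail p = 0.0128, 0.0256 doubled) and reported with its exact 95% confidence interval. Separately, the study meets its effectiveness criterion only if at least 6 of 10 subjects respond (section 6); 4 or 5 responders is significant against 10% but does not meet the criterion.*

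Beside the stated 0.80 in the power paragraph, add that at a true 60% rate this test has power 0.945 and the probability of meeting the 6/10 criterion is 0.633. Give the method behind 0.80 or replace it.

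The cost is one sentence replaced and one added, both in section 13. The sample size, the data collected and the 6/10 criterion stay as they are. The tic score that defines a responder should be reconciled separately, so that the new sentence does not inherit that conflict.
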